
6.0 CRITERIA FOR PARTICIPANT ELIGIBILITY

6.1 Participant Inclusion Criteria

1. Patients must be enrolled or agree to consent to the companion genomic profiling study MSKCC IRB# 12-245 Part A. Results are not required prior to

Memorial Sloan Kettering Cancer Center
[name]
[name]

initiating treatment on protocol, unless patients do not have other test results by IHC or FISH confirming HER2 overexpression.

2. Patients must have recurrent or persistent HER2 overexpressing endometrial cancer or endometrial carcinosarcoma. HER2 overexpression is defined as 3+ by IHC or 2+ with gene amplification by FISH (HER2/CEP17 ratio ≥ 2) or HER2 amplified (fold change ≥ 2) on MSK IMPACT.
3. Histologic documentation of diagnosis of endometrial carcinoma or carcinosarcoma is required.
4. Age ≥ 18 years
5. Patients must have had at least one but no more than two prior chemotherapeutic regimens for management of endometrial carcinoma (including neo-adjuvant and/or adjuvant chemotherapy). Initial treatment may include chemotherapy, chemotherapy and radiation therapy, and/or consolidation/maintenance therapy. Chemotherapy administered in conjunction with primary radiation as a radio-sensitizer WILL be counted as a systemic chemotherapy regimen. Prior hormonal therapy will **not** count as a prior regimen.
Prior treatment with trastuzumab is allowed.
6. Eastern Cooperative Oncology Group (ECOG) performance status of 0 or 1.
7. LVEF $\geq 50\%$ on baseline screening ECHO.
8. Resolution of adverse effects of recent surgery, radiotherapy, or chemotherapy to Grade ≤ 1 prior to first study treatment (with the exception of alopecia or clinically insignificant laboratory values).
9. Patients must have measurable disease. Measurable disease is defined by RECIST (version 1.1). Measurable disease is defined as at least one lesion that can be accurately measured in at least one dimension (longest diameter to be recorded). Each non-nodal lesion must be ≥ 10 mm when measured by CT, MRI or caliper measurement by clinical exam; or ≥ 20 mm when measured by chest x-ray. Lymph nodes must be ≥ 15 mm in short axis when measured by CT or MRI.
10. No active infection requiring antibiotics (with the exception of uncomplicated urinary tract infection).
11. All patients must consent to mandatory pre-treatment and post-treatment core needle biopsies.
12. Patients must have adequate hematological, liver, cardiac and kidney function within 14 days prior to first treatment:

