9.0 PRE-TREATMENT/INTERVENTION

Screening Visit

In some cases, clinical assessments performed prior to obtaining informed consent may be used to qualify the patient for the study. These include radiological tumor assessment, physical examinations, hematology, serum chemistry results, coagulation studies, urinalysis, or other assessments which may be considered part of normal standard of care. In these cases, repeat assessments may not be necessary prior to enrollment, unless individual parameters require further study or confirmation and are clinically appropriate.

Within 28 days prior to treatment start:

- Written informed consent
- History and Physical examination
- Review of concomitant medications
- Vital signs (blood pressure, heart rate and temperature), weight and height
- ECOG Performance status
- Toxicity assessment
- 12-lead ECG
- Echocardiogram
- Radiographic tumor measurements (CT C/A/P, MRI)
- Screening Biopsy (3 Cores) if deemed safe and feasible (Refer to: Exploratory Correlative Studies section for details)
- Patients must have documented HER2 overexpression, defined as 3+ by IHC or 2+ with gene amplification by FISH (HER2/CEP17 ratio ≥ 2) or HER2 amplified (fold change ≥ 2) on MSK IMPACT any time prior to starting treatment
- Hepatitis B Testing, if not done previously at MSK to rule out active infection (see exclusion criteria for details)

Within 14 days prior to treatment start:

- Complete Blood Count (CBC) with differential
- Comprehensive profile (BUN, creatinine, sodium, potassium, chloride, CO2, calcium, glucose, total bilirubin, total protein, albumin, alkaline phosphatase, AST, ALT)
- Coagulation tests: Prothrombin time, APTT and INR (PT/PTT)
- Magnesium
- Uric Acid
- Urinalysis
- Pregnancy test (in women of childbearing potential)
 - Women of child bearing potential (WCBP), defined as a sexually mature woman who has not undergone surgical sterilization or who has not been naturally postmenopausal for at least 12 consecutive months (i.e., who has had menses any time in the preceding 12 consecutive months) must agree to use effective

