3. Mandatory pre-treatment and post-treatment tumor biopsies will be obtained on all patients to assess *HER2* expression, its association with treatment response and other genetic changes over time. Attempts will be made to collect 3 cores (Flash Frozen) of tumor material at each time point for research purposes under the current study. Biopsies will only be performed if deemed safe and feasible by the investigator. Post-treatment biopsy will only be done upon progression of disease. Tissue testing will be performed in the CMO. To determine mutational status and/or copy number variations of relevant cancer related genes using MSK-IMPACT platform in patients with response to therapy. MSK-IMPACT tests will be done on new biopsy specimens for research purposes in the context of this protocol. Results from these testing will not be reported to patients.
4. To determine the ability of the laboratory parameters to predict clinical benefit:
 - a. All patients will undergo mandatory pre-treatment fresh tumor biopsy (if deemed clinically safe). Post-treatment fresh tumor biopsy will be done upon disease progression.
5. To evaluate the predictive value of changes in circulating tumor DNA variant allele frequency during treatment for response to ZW25. Circulating plasma cell-free DNA will be collected at pre-treatment (any time prior to C1D1), and at End of Treatment. MSK's standard cfDNA workflow will be followed (one streck tube).
 - a. Liquid biopsy through the sequencing of plasma ctDNA has the potential to address multiple biologic questions, including global tumor heterogeneity. Targeted deep sequencing of candidate driver oncogenes facilitates analysis of the clonal structure of the tumor, and prioritization of clinically relevant actionable targets. As blood content theoretically integrates mutational data from all sites of disease, deep analysis of plasma ctDNA may offer a solution to the problem of assessing intratumoral heterogeneity with tumor biopsies, and ultimately could define a systemic genomic approach to guide application of targeted therapies. A novel bioinformatics algorithm called FACETS developed at Memorial Sloan Kettering will be applied to interrogate clonality from targeted sequencing of ctDNA.

Whole genome or whole exome sequencing will not be done in this study unless activity is seen after data review, at which point the protocol may be amended to include additional objectives.

Incidental Inherited Genomic Findings:

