13.0 CRITERIA FOR OUTCOME ASSESSMENT AND ENDPOINT EVALUABILITY

13.1 Criteria for Therapeutic Response/Outcome Assessment

RESPONSE DEFINITION (RECIST 1.1)⁴⁸

DEFINITIONS:

Baseline: Baseline is defined as the most recent assessment performed prior to the first dose of study treatment. Baseline assessments must be performed within the period defined in the protocol eligibility criteria.

Memorial Sloan Kettering Cancer Center
[name]
[name]

Measurable Lesions: Except for lymph nodes (described below), measurable lesions are defined as those that can be accurately measured in at least one dimension (longest diameter to be recorded) as ≥ 10 mm with CT scan (if CT scans have slice thickness greater than 5 mm, the minimum size of a measurable lesion is twice the slice thickness).

- To be considered pathologically enlarged and measurable, a lymph node must be ≥ 15 mm in short axis when assessed by CT scan (CT scan slice thickness recommended to be no greater than 5 mm). At baseline and in follow-up, only the short axis will be measured and recorded.
- MRI may be substituted for contrast-enhanced CT for lesions at some anatomical sites, but not for lesions in the lungs. The minimum size for measurability is the same as for CT (10 mm) as long as the scans are performed with slice thickness of 5 mm and no gap. If MRI is performed with thicker slices, the size of a measurable lesion at baseline should be twice the slice thickness. In the event there are inter-slice gaps, this also needs to be considered in determining the size of measurable lesions at baseline.

Non-measurable lesion: all other lesions (or sites of disease) including small lesions (longest diameter <10 mm or pathological lymph nodes with ≥ 10 to < 15 mm short axis), are considered non-measurable.

- Lymph nodes that have a short axis < 10 mm are considered non-pathological and are not to be recorded or followed.
- Bone lesions, leptomeningeal disease, ascites, pleural/pericardial effusions, lymphangitis cutis/pulmonitis, inflammatory breast disease, and abdominal masses (not followed by CT or MRI), are considered as non-measurable.

Target lesions:

All measurable lesions up to a maximum of 2 lesions per organ and 5 lesions in total, representative of all involved organs, are to be identified as target lesions and measured and recorded at baseline.

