- Target lesions are to be selected on the basis of their size (lesions with the longest diameter) to represent all involved organs, and to be those that lend themselves to reproducible repeated measurements.
- It may be the case that on occasion, the largest lesion does not lend itself to reproducible measurement in which circumstance the next largest lesion which can be measured reproducibly should be selected.

Memorial Sloan Kettering Cancer Center
[name]
[name]

- Target lesions will be measured at each assessment (longest axis for non-nodal lesions, shortest axis for measurable malignant nodal lesions).

Non-target lesions: All other lesions (or sites of disease) including all non-measurable lesions (including pathological lymph nodes with ≥ 10 to < 15 mm short axis) and all measurable lesions over and above the 5 target lesions are to be identified as non-target lesions and recorded at baseline.

- Measurements of these lesions are not required, but the presence, absence, unequivocal progression of each is to be recorded throughout follow-up.
- Lymph nodes that have a short axis < 10 mm are considered non-pathological and are not to be recorded or followed.

Special Considerations

Clinical Examination of Lesions: Superficial or visible lesions that cannot be assessed by CT scan or MRI will only be considered for response assessment if these lesions are biopsy-proven metastatic lesions and ≥ 10 mm in diameter. These lesions will be considered non-measurable and thus non-target for response assessment.

Cystic lesions: Cystic lesions thought to represent cystic metastases can be considered as measurable lesions if they meet the definition of measurability described above. However, if non-cystic lesions are present in the same patient, these are preferred for selection as target lesion.

Bone lesions: Bone scan, PET scan or plain films are not considered adequate imaging techniques to measure bone lesions. However, these techniques can be used to confirm the presence or disappearance of bone lesions.

- Lytic bone lesions or mixed lytic-blastic lesions, with identifiable soft tissue components, that can be evaluated by cross-sectional imaging techniques such as CT or MRI can be considered as measurable lesions if the soft tissue component meets the definition of measurability described above.
- Blastic bone lesions are non-measurable.

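### The caliper route to measurable disease in criterion 9 conflicts with Section 13.1, so a patient whose only lesion cannot be imaged could count as a responder only through CR

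*Combined protocol and SAP*

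**What the plan says.** Section 6.1, criterion 9, requires measurable disease and refers to RECIST: "Measurable disease is defined by RECIST (version 1.1"). It then writes out its own thresholds. For lesions outside lymph nodes it says: "Each non-nodal lesion must be ≥ 10 mm when measured by CT, MRI or caliper measurement by clinical exam".

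Section 13.1 is also presented as RECIST 1.1. It defines a measurable non-nodal lesion as at least 10 mm on CT, with MRI as a substitute at some sites, and gives no caliper route. Under Clinical Examination of Lesions it states: "Superficial or visible lesions that cannot be assessed by CT scan or MRI will only be considered for response assessment", and adds the condition "if these lesions are biopsy-proven metastatic lesions and ≥ 10 mm in diameter". It then fixes their status: "These lesions will be considered non-measurable and thus non-target for response assessment". Under Imaging Methods it foresees lesions that can be followed only by clinical examination, with biopsy-proven visible lesions at the vaginal apex as the example.

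Section 14.1 defines response as a best overall response of CR or PR within 24 weeks. It drops from the efficacy population only treated patients with no post-baseline response assessment. Section 14 defines CBR as CR + PR + SD.

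**The concern.** One lesion can be measurable for entry and non-measurable for the primary endpoint. Staff checking eligibility would read criterion 9, and those assessing response would read Section 13.1. If a patient's only qualifying lesion is one that CT and MRI cannot assess, PR and SD are closed to her, because both are defined on the sum of target-lesion diameters. A large but incomplete shrinkage would be scored as a non-response and still sit in the denominator. With 25 patients and a success threshold of 5 responses, each patient is 4 percentage points of ORR (1/25).

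**Working it through.** **1. Response categories open to the patient.** With no target lesion at baseline, the target response in Section 13.1 is N/A. The table for overall response then gives:

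| Target | Non-target | New lesion | Overall | In ORR? | In CBR (literal)? |
|---|---|---|---|---|---|
| N/A | CR | No | CR | Yes | Yes |
| N/A | Non-CR/non-PD | No | Non-CR/non-PD | No | No |
| Any | PD | Any status | PD | No | No |
| Any | Any | Yes | PD | No | No |

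UE is also possible when assessment is incomplete. No row with target N/A leads to PR or SD. Once she has a post-baseline assessment, Section 14.1 keeps her in the efficacy population.

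**2. The plan's own figure.** Inputs from Section 14.1: 16 patients in stage 1, continue with at least 2 responses; 25 in total, positive with at least 5; rates of 10% and 30%; type I error 10%; power 90%. The exact calculation is

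P(positive) = Σ over x from 2 to 16 of P(X1 = x) × P(X2 ≥ 5 − x), with X1 ~ Bin(16, p) and X2 ~ Bin(9, p).

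- p = 0.30: 0.9030, so the stated 90% power reproduces.
- p = 0.10: 0.0951, within the 10% limit.

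**3. One affected patient (an assumption, not in the documents).** She responds, by CR only, with probability q. The other 24 respond with probability p. If she is in stage 1, X1 is Bin(15, p) plus one Bernoulli(q); if in stage 2, X2 is Bin(8, p) plus one Bernoulli(q). She falls in stage 1 with weight 16/25 and in stage 2 with weight 9/25.

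Power at p = 0.30 and q = 0:
- in stage 1: 0.8802
- in stage 2: 0.8843
- weighted: 0.64 × 0.8802 + 0.36 × 0.8843 = 0.8817

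Expected ORR is 24 × 0.30 / 25 = 28.8%, against 30%.

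Type I error with the other 24 at p = 0.10:
- q = 0: 0.0825
- q = 0.10: 0.0951, unchanged, because she then responds like everyone else
- q = 0.15: 0.101

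The error rate increases with q, so it does not exceed 0.0951 as long as q is at most 10%.

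**The case against.** The strongest defence is that criterion 9 starts from RECIST 1.1 and Section 13.1 is the protocol's own RECIST 1.1 text. All patients also have CT or MRI at screening and a baseline classification into target and non-target lesions, so a patient without a target lesion should be noticed. This makes such an enrolment less likely. It does not remove the conflict, because criterion 9 spells out the caliper route and does not require a target lesion under Section 13.1.

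It can also be said that the response table does cover patients with no target lesion. For ORR that is right: the rule is strict but defined. For CBR, Section 14 lists CR, PR and SD and is silent on non-CR/non-PD, so its exclusion is the literal reading rather than a stated rule.

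Three stronger readings are tempting, and the documents do not support them.

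- *Any lesion measured by caliper is lost to response assessment.* The exclusion covers only lesions that CT and MRI cannot assess. A palpable lesion that also measures at least 10 mm on imaging can still be a target lesion.
- *A patient whose lesion is not biopsy-proven has no defined analysis population.* A reader might infer this because the screening biopsy is qualified: "Screening Biopsy (3 Cores) if deemed safe and feasible" in Section 9.0, and "Biopsies will only be performed if deemed safe and feasible by the investigator" in Section 10.0. But criterion 11 requires consent to a mandatory pre-treatment biopsy, and the Section 11.0 schedule lists both that biopsy and confirmation of the diagnosis from fresh tissue. The vaginal-apex example in Section 13.1 is itself limited to biopsy-proven lesions, and that section also has all non-measurable lesions recorded as non-target. What is left is a theoretical residual case.
- *The effect can only be conservative.* This holds for type I error only if her chance of CR is at most 10%.

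**Conclusion.** The inconsistency is real and minor. Criterion 9 can admit a patient on a lesion that Section 13.1 makes non-target, and she could then count toward ORR only through CR while staying in the denominator. The same applies to CBR if its CR + PR + SD definition is taken literally.

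The size depends on how many such patients enrol, which the documents do not give. If none enrols, there is no effect. One such patient with no chance of CR costs about 2 points of power (90.3% to 88.2%), with the other 24 responding at 30%. The two-stage design itself reproduces and is not in question. The documents give no ground for saying that the trial is underpowered or that its ORR will be biased in practice.

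**What to change.** Reconcile criterion 9 with the measurability rules in Section 13.1, so that every enrolled patient has at least one lesion at baseline that qualifies as a target lesion under Section 13.1. One sentence in criterion 9 would do this, with no change to the sample size or decision rule. It would also remove the residual case of a lesion that is neither imageable nor biopsy-proven. The cost is that a few patients with only visible disease that cannot be imaged would not be eligible.

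If those patients are to remain eligible, Section 14 should state how non-CR/non-PD counts in ORR and in CBR, and the report should give their number. That excludes no one, but response then means something different for those patients than for the rest.

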6.2 Participant Exclusion Criteria

1. Women who are pregnant or lactating or women of childbearing potential (WCBP) not protected by highly effective contraceptive methods.
2. > Grade 1 peripheral neuropathy.
3. History of hemorrhagic or ischemic stroke within the prior six months.
4. History of NYHA Class II-IV heart failure, no serious arrhythmia.
5. History of MI or unstable angina within 6 months of study initiation.

6. Patients with a lifetime cumulative dose of anthracycline >300 mg/m² or who have received anthracycline treatment within 90 days of the expected first dose of ZW25 are not eligible for treatment.
7. Prior hypersensitivity to monoclonal antibodies.
8. Active hepatitis B or hepatitis C infection. Patients with previously resolved hepatitis B infection are eligible. Presence of positive test results for hepatitis B infection who have resolved the infection (defined by positive for HB surface antibody (anti-HBs) and polymerase chain reaction (PCR) assay is negative for HBV DNA are eligible. Patients positive for HCV antibody are eligible only if testing for HCV RNA is negative.
9. Known HIV infection.
10. Current severe, uncontrolled systemic disease (e.g., clinically significant cardiovascular, pulmonary, or metabolic disease).
11. Major surgical procedure or significant traumatic injury within 28 days prior to Day 1 or anticipation of the need for major surgery during the course of study treatment.
12. Known untreated or active central nervous system (CNS) metastases (progressing or requiring anticonvulsants or corticosteroids for symptomatic control) leptomeningeal carcinomatosis.

Patients with a history of treated CNS metastases are eligible, provided that they meet all of the following criteria:

- a. Presence of measurable disease outside the CNS
- b. No radiographic evidence of worsening upon the completion of CNS-directed therapy and no evidence of interim progression between the completion of CNS-directed therapy and the screening radiographic study
- c. No history of intracranial hemorrhage or spinal cord hemorrhage
- d. No ongoing requirement for dexamethasone as therapy for CNS disease (anticonvulsants at a stable dose are allowed)
- e. Absence of leptomeningeal disease

13. Inability to comply with study and follow-up procedures.
14. Known allergy or hypersensitivity to the components of ZW25 formulation.
15. Any other disease, metabolic dysfunction, physical examination finding, or clinical laboratory finding that, in the investigator's opinion, gives reasonable suspicion of a disease or condition that contraindicates the use of an

investigational drug or that may affect the interpretation of the results or render the patient at high risk from treatment complications.

16. Active or history of inflammatory bowel disease (IBD)
17. Severe infections within 4 weeks prior to initiation of study drug treatment, including but not limited to hospitalization for complications of infection, bacteremia, or severe pneumonia.
18. Treatment with therapeutic oral or IV antibiotics within 2 weeks prior to initiation of study treatment. Patients receiving prophylactic antibiotics (e.g., for prevention of urinary tract infection or to prevent chronic obstructive pulmonary disease exacerbation) are eligible for the study. Patients receiving antibiotic treatment for urinary tract infection are also eligible.
19. Administration of a live attenuated vaccine within 4 weeks prior to initiation of study treatment or anticipated need for such a vaccine during study. Patients must agree not to receive live, attenuated influenza vaccine (e.g., Flumist®) within 4 weeks prior to treatment.)
20. Participation in another clinical study with receipt of an investigational product during the last 4 weeks.
21. History of another primary malignancy except for:
 - a. Malignancy treated with curative intent and with no known active disease ≥ 2 years before the first dose of study drug and of low potential risk for recurrence.
 - b. Adequately treated non-melanoma skin cancer or lentigo maligna without evidence of disease.
 - c. Adequately treated carcinoma in situ without evidence of disease (e.g., cervical cancer in situ).
 - d. Adequately treated stage 1 breast cancer.
22. Receipt of the last dose of anti-cancer therapy (chemotherapy, immunotherapy, targeted therapy, biologic therapy, tumor embolization, monoclonal antibodies) < 21 days prior to the first dose of study drug. Receipt of the last dose of hormonal therapy within < 7 days prior to the first dose of study drug.
23. Any prior radiation therapy must be discontinued at least four weeks prior to registration.
24. QT interval corrected for heart rate (QTc) ≥ 470 ms on screening electrocardiograms (ECG) using QTC Federica.

Memorial Sloan Kettering Cancer Center
[name]
[name]

25. History of small or large bowel obstruction within 3 months of registration, including subjects with palliative gastric drainage catheters. Subjects with palliative diverting ileostomy or colostomy are allowed if they have been symptom free for more than 3 months.
26. Subjects with refractory ascites, defined as ascites needing drainage catheter or therapeutic paracentesis more often than every 4 weeks.
27. Ongoing bowel perforation or presence of bowel fistula or abscess within 3 months of registration.

